## Appendix 4 Clinical Laboratory Tests

The tests detailed in [Table 1](#) will be performed by the local laboratory.

Protocol-specific requirements for inclusion or exclusion of participants are detailed in Sections [5.1](#) and [5.2](#), respectively, of the protocol.

Additional tests may be performed at any time during the study as determined necessary by the Investigator or required by local regulations.

**Table 1 Protocol-Required Safety Laboratory Assessments**

All study-required laboratory assessments will be performed by a local laboratory:

Laboratory Assessments	Parameters

 
• Hematology
 
	
 
• Leucocytes, erythrocytes, hemoglobin, hematocrit, platelets, differential count (neutrophils, eosinophils, basophils, monocytes, lymphocytes), mean corpuscular hemoglobin (MCH), mean corpuscular hemoglobin concentration (MCHC) and reticulocyte counts.
 

 
• Clinical Chemistry
 
	
 
• Alanine aminotransferase (ALT), aspartate aminotransferase (AST), total, direct and indirect bilirubin, alkaline phosphatase (ALP), gamma glutamyl transferase (at screening only), creatinine phosphokinase (at screening only), total protein, albumin, urea, creatinine, creatinine clearance (CrCl) (at screening and Day –1 only using the Cockcroft-Gault formula), uric acid, fasting glucose, sodium, chloride, potassium, calcium, phosphorus.
 

 
• Coagulation
 
	
 
• INR, aPTT, PT.
 

 
• Viral Serology
 
	
 
• Hepatitis A virus (HAV IgM Ab), hepatitis B virus (HBsAg and HBcAb), hepatitis C virus (HCV RNA or HCV Ab), human immunodeficiency virus (HIV-1 and HIV-2 Ab).
 

 
• Lipids
 
	
 
• Cholesterol, LDL cholesterol, HDL cholesterol, triglycerides.
 

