### **Table 1 Schedule of Activities – Main Table (cont.)**

- a. A full physical exam is required at screening, follow-up and early treatment termination visits. At subsequent visits (or as clinically indicated), limited, symptom-directed physical examinations should be performed at the discretion of the Investigator. Height will only be recorded at screening. BMI will be calculated at screening.
- b. Vital signs include triplicate measurements of blood pressure and pulse rate and single assessment of body temperature (tympanic or oral). Blood pressure and pulse measurements will be assessed after at least 5 minutes in a supine position.
- c. Twelve-lead ECGs will be obtained in triplicate (three consecutive interpretable 12-lead ECGs in less than 5 minutes) after the participant has been in a supine position for at least 10 minutes. Automated ECG intervals (PR [PQ], QRS, QT, QTcF, RR) and HR will be captured or calculated, and the changes in T-wave and U-wave morphology will be documented.
- d. Samples for clinical laboratory tests (hematology, chemistry, coagulation, urinalysis) should be collected in the morning of Period 1 Day 4 and Period 2 Day 7 approximately the same time as the 72 hour (Period 1 Day 4) or 12 hour (Period 2 Day 7) post-dose PK samples are collected. At all other time points these samples should be taken at the most appropriate time.
- e. Hepatitis A (HAV IgM Ab), total Hepatitis B Core Antibody (HBcAb), Hepatitis B (HBsAg), Hepatitis C (HCV RNA or HCV Ab), human immunodeficiency virus (HIV-1 and HIV-2 Ab).
- f. Serum or plasma beta-human chorionic gonadotropin ( $\beta$ -HCG) at screening, urine on all other occasions (females only). If urine is positive, then need confirmatory serum or plasma test.
- g. Follicle stimulating hormone (females only; to confirm post-menopausal status).
- h. If the genetic blood sample is not collected at Day 1, it may be collected at any time during the conduct of the clinical study.
- i. RBR blood sample will be collected at pre-dose Period 1.
- j. The participant will discharge in the morning after all the samples for the PK and safety assessments have been taken and the participant has the option to stay in clinic during the whole Period 1 and wash-out period if agreed by Sponsor and the Investigator (i.e., discharge Period 2, Day 7).
- k. A washout period of at least 7 days, but not more than 21 days, between the two periods. Washout period is defined as from Period 1 Day 1 to Period 2 Day 1.

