### **2.2.3 Background on Pitavastatin**

Pitavastatin is an approved HMG-CoA reductase inhibitor (i.e., statin), used in the treatment of hypercholesterolemia. Statins have been shown to reduce cardiovascular morbidity and mortality, and their efficacy and safety for the primary and secondary prevention of cardiovascular events have been demonstrated in a large number of clinical trials.

Dose-proportional increases in pitavastatin  $C_{max}$  and  $AUC_{inf}$  were observed following daily administration ranging from 1 to 24 mg. Given with a high-fat and high-calorie meal,  $C_{max}$  decreased by 43% but the AUC did not decrease significantly. The mean plasma elimination half-life ( $t_{1/2}$ ) is approximately 12 hours (LIVALO® U.S. Package Insert). Per the transporter expressing HEK293 cells and human cryopreserved hepatocytes, the OATP1B1 and OATP1B3 transporter account for almost all the observed pitavastatin uptake clearance into human hepatocytes and OATP1B1 accounts for about 90% of the clearance (Hirano et al 2004). Pitavastatin has been reported to be sensitive to OATP1B inhibition (Prueksaritanont et al 2014).

Pitavastatin was generally well-tolerated in clinical trials of up to 60-week duration, with a tolerability profile broadly similar to that of atorvastatin and simvastatin (Duggan 2012). The adverse-events (AE) profile of pitavastatin compares favorably with those of other available statins. Reported AEs of pitavastatin included gastrointestinal symptoms (0.7%–2.2%), myopathies (0.3%–1.1%), and elevated hepatic enzyme concentrations (0.0%–8.8%; Yee et al 2011).

A detailed description of the chemistry, pharmacology, efficacy and safety of pitavastatin is provided in the pitavastatin package insert hours (LIVALO® U.S. Package Insert).

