### **2.3 BENEFIT/RISK ASSESSMENT**

This study has the principal aim of characterizing the drug-drug interaction between RO7049389 and an OATP substrate, the cholesterol-lowering drug pitavastatin, a representative of the statin class, in a population of healthy volunteers. There will be no therapeutic benefit for the healthy volunteers participating in the study. However, assessment of the influence of RO7049389 on the safety and PK of pitavastatin brings valuable information for the development of RO7049389. The target population could be exposed to statins or other OATP1B1 substrates, therefore, the results from the study will provide essential information to guide dosing of statins when co-administered with RO7049389.

The risks for the individual participant due to exposure to RO7049389 and/or pitavastatin or study-related procedures are considered acceptable or low in this study.

[REDACTED]

The risks

associated with two administrations of 2 mg single dose of pitavastatin in this study are also considered acceptable or low due to extensive clinical experience with pitavastatin at doses up to 24 mg and over much longer treatment durations, up to 60 weeks (Duggan 2012). In addition, careful safety monitoring of all critical safety parameters will be performed throughout this study and there will be close monitoring of all participants during dosing and in-clinic stay.

More detailed information about the known and expected benefits in the context of potential risks and reasonably expected adverse events of RO7049389 is provided in the [RO7049389 Investigator's Brochure](#).

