**Table 3 Objectives and Endpoints**

Objectives	Endpoints
Primary	

 
To determine the effect of multiple-doses of RO7049389 on the single-dose pharmacokinetics (PK) of pitavastatin in healthy participants.
 
	
 
Primary PK parameters of pitavastatin: <math>C_{max}</math>, and <math>AUC_{0-inf}</math>
 
Secondary PK parameters of pitavastatin: <math>t_{max}</math>, CL/F, V/F and <math>t_{1/2}</math>.
 
Other parameters may be calculated if considered appropriate.
 

Secondary	

 
To evaluate the safety and tolerability of the single-dose pitavastatin alone and in combination with multiple-doses of RO7049389 in healthy participants.
 
To explore the effect of the single-dose of pitavastatin on steady-state PK of RO7049389 in healthy participants.
 
To determine the effect of multiple-doses of RO7049389 on the single-dose PK of pitavastatin lactone in healthy participants (if applicable).
 
	
 
Incidence and severity of adverse events.
 
Incidence of laboratory abnormalities based on hematology, clinical chemistry, coagulation, lipids, and urinalysis test results.
 
ECGs.
 
Vital signs including blood pressure (BP), pulse rate and body temperature.
 
Primary PK parameters of RO7049389 and its metabolites (RO7121986, RO7255420 and RO7255422): <math>C_{max}</math>, and <math>AUC_{tau}</math>.
 
PK parameters of pitavastatin lactone: <math>C_{max}</math>, and <math>AUC_{0-inf}</math>.
 
The AUC ratio of pitavastatin lactone/pitavastatin.
 

Exploratory	

 
To evaluate the effect of multiple-doses of RO7049389 on OATP activity as assessed by plasma and urine coproporphyrins (CP-I and CP-III).
 
	
 
Coproporphyrins (CP-I and CP-III) AUC in plasma and amount excreted in urine.
 

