### **4.2 SCIENTIFIC RATIONALE FOR STUDY DESIGN**

The study rationale is provided in Section [2.1](#).

This is an open-label, fixed sequence, two-period study.

The primary objective of this study is to determine the effect of multiple-doses of RO7049389 on the single-dose PK of pitavastatin in healthy participants. As PK measurements are objectively analysed an open-label study design has been chosen. To minimize the number of participants needed and reduce inter-subject variability, this study will follow a two-period instead of parallel design. The duration of both washout and drug administration periods was established on the basis of the known

pharmacokinetic profiles of both RO7049389 and pitavastatin. The half-life [REDACTED] of RO7049389 was used to calculate the likely time needed for steady state and that of pitavastatin was used to calculate the duration needed to capture its entire elimination phase. To ensure the full potential for an interaction is realized (maximal inhibition of OATP), pitavastatin will be co-administered with RO7049389 while the latter is in steady state. Administration of RO7049389 will be continued throughout the whole elimination phase of pitavastatin. Accordingly, a fixed sequence design has been chosen for logistical reasons.

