#### **4.2.2 Rationale for Biomarker Assessments**

Coproporphyrins (CP-I and CP-III) AUC ratios in plasma and amount excreted in urine ratios will be measured as endogenous markers for hepatic OATP1B1 inhibition. CP-I and III are porphyrin metabolites arising from heme synthesis and eliminated through bile and urine. CP-I and CP-III in plasma and the amount excreted in urine are reported to be substrates of OATP1B1 and OATP1B3 (Yurong Lai et al., 2016).

Correlation between pitavastatin clearance and endogenous substances will be explored in this study. If OATP1B1 activity needs be monitored for future RO7049389 clinical studies, the Coproporphyrins (CP-I and CP-III) AUC in plasma and/or amount excreted in urine, instead of pitavastatin, can be conveniently employed in such studies.

[REDACTED]

[REDACTED]

[REDACTED]

[REDACTED]

[REDACTED]

RO7049389 will be administered for 6 days with concurrent administration on Day 4 with pitavastatin and any possible OATP inhibition is at its maximum at steady state.

Pitavastatin was approved at dose range of 1 mg to 4 mg once daily. As potential OATP1B1 mediated exposure increase cannot be excluded when given in combination with RO7049389, a single dose of 2 mg of pitavastatin was chosen in this study considering the demonstrated safety and linear pharmacokinetics PK across a dose range of 1 mg to 24 mg following single dose.

The dosing periods selected for this study have been chosen to ensure that steady state will have been reached for RO7049389, and any possible significant drug-drug interaction will be detected, whilst minimizing exposure to any drug to the shortest period necessary.

Further details are provided in the [RO7049380 Investigator's Brochure](#)

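### Creatine phosphokinase is scheduled at screening only, so symptomless changes cannot be compared between pitavastatin alone and pitavastatin with RO7049389

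*Combined protocol and SAP*

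**What the plan says.** **Objective and endpoint.** Section 3, Table 3 sets a secondary objective: "To evaluate the safety and tolerability of the single-dose pitavastatin alone and in combination with multiple-doses of RO7049389 in healthy participants". One of its endpoints is "Incidence of laboratory abnormalities based on hematology, clinical chemistry, coagulation, lipids, and urinalysis test results".

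**CPK.** Appendix 4, Table 1 lists the chemistry panel with this restriction: "gamma glutamyl transferase (at screening only), creatinine phosphokinase (at screening only"). No other section schedules CPK. The Schedule of Activities (Section 1.3, Table 1) has a blood chemistry row but does not name analytes.

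**Chemistry draws.** That row is marked at screening; Period 1 Days -1 and 4; Period 2 Days -1, 4 and 7; follow-up; and early termination. Footnote d fixes two of these times: "Samples for clinical laboratory tests (hematology, chemistry, coagulation, urinalysis) should be collected in the morning of Period 1 Day 4 and Period 2 Day 7".

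**Why muscle is relevant.** Section 2.2.3 gives a rate for muscle disorders among pitavastatin's reported adverse events ("myopathies (0.3%–1.1", in per cent). Section 4.2 explains why pitavastatin is given at RO7049389 steady state: "To ensure the full potential for an interaction is realized (maximal inhibition of OATP"). The dose rationale, which follows Section 4.2.2, begins: "As potential OATP1B1 mediated exposure increase cannot be excluded when given in combination with RO7049389". Section 2.3 states that "careful safety monitoring of all critical safety parameters will be performed throughout this study".

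**The concern.** The plan measures CPK once, before any drug, and then makes chemistry abnormalities an endpoint for pitavastatin alone and in combination. A laboratory endpoint needs a value after dosing. Without one, an empty CPK column in the report means that nothing was measured, and it could be misread as evidence of no muscle effect. Section 2.3 says the results will guide statin dosing alongside RO7049389, so a symptomless enzyme rise on the combination is something readers of the report may look for. A participant who did develop muscle symptoms would also have no recent scheduled value for comparison.

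The documents do not themselves say that CPK is a muscle enzyme. I take that as general clinical knowledge.

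**Working it through.** The plan states no figure to reproduce. The check is a count of scheduled values and the age of the one that exists.

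**1. Scheduled CPK values after a dose.** The chemistry row has five draws after the first pitavastatin dose: Period 1 Day 4, Period 2 Days -1, 4 and 7, and follow-up. CPK is reported from 0 of 5.

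**2. Which draws follow which treatment.**

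| Draw | Position |
|---|---|
| Period 1 Day 4 | about 72 h after pitavastatin alone |
| Period 2 Day -1 | after washout, before RO7049389 |
| Period 2 Day 4 | during RO7049389; time not fixed, presumably before the combination dose (Section 8.10.2) |
| Period 2 Day 7 | about 72 h after the combination dose (Day 7 − Day 4 = 3 days) |
| Follow-up | after all dosing |

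Only two of the five clearly follow the combination dose. Period 1 Day 4 and Period 2 Day 7 form a matched pair at the same delay after pitavastatin.

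**3. Age of the screening value at co-administration.** Age = (days from screening to Period 1 Day 1) + (washout, Period 1 Day 1 to Period 2 Day 1) + (Period 2 Day 1 to Day 4).

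- Shortest: 2 + 7 + 3 = 12 days.
- Longest: 28 + 21 + 3 = 52 days.

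The Period 2 Day -1 sample, already drawn, would be 1 + 3 = 4 days old.

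**4. Effect on the planned output.** Appendix 4 counts a marked abnormality when a value lies outside the marked range and has also changed from baseline by a defined amount. With no later value, no CPK change, flag or between-period comparison can be derived.

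**5. What 18 participants could show.** The chance of at least one event is 1 − (1 − p)^N, with p from Section 2.2.3 and N from Section 9.2.

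| p | N = 16 | N = 18 |
|---|---|---|
| 0.3% | 4.7% | 5.3% |
| 1.1% | 16.2% | 18.1% |

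Zero events in 18 would leave a one-sided 95% upper bound of 1 − 0.05^(1/18) = 15.3%. These rates are for myopathies, and Section 2.2.3 does not say that they come from single doses. The documents give no rate for symptomless CPK rises. If that rate were 5% to 20% (an assumption), the chance of at least one among 18 would be 60% to 98%.

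**The case against.** The strongest reply is that muscle safety is already covered and the exposure is small.

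- **Adverse events.** They are the first endpoint for the same objective. They are collected for 28 days after the last dose (Section 8.3.1), by non-leading questioning (Section 8.3.2), and summarised by period (Table 6). Symptomatic myopathy falls there. This stands.
- **Extra tests.** Section 8.2.4, Section 8.10.5 and Appendix 4 let the investigator add tests, and Appendix 2 requires supplemental evaluation of adverse events where medically indicated. This stands for a participant with symptoms. It gives no systematic incidence and is unlikely to find a silent rise.
- **Exposure.** Pitavastatin is given twice, 2 mg each time. The dose rationale chose 2 mg because exposure might rise, citing safety and linear kinetics from 1 to 24 mg; the top of that range is 12 times the study dose. This limits the practical weight.
- **Other pointers.** On general clinical knowledge, AST and dipstick blood can change with muscle injury, and both are repeated. They are nonspecific and do not replace CPK.

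Four stronger readings are tempting, and the documents do not support them.

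- A reader might infer that the trial is blind to any muscle effect, or that its safety objective goes unanswered. Adverse-event collection and discretionary testing rule that out.
- A reader might infer that the design sets out to raise pitavastatin exposure. It seeks maximal OATP inhibition, but describes the exposure increase as possible only.
- A reader might infer that CPK alone was singled out. Gamma glutamyl transferase is also limited to screening, and creatinine clearance to screening and Day -1.
- A reader might infer that Section 2.3 is contradicted. It does not define its critical parameters or name CPK, and parts of Section 2.3 and the dose rationale are redacted.

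**Conclusion.** The point holds in a limited form. No scheduled CPK value follows any dose, and the only required one is 12 to 52 days old at co-administration. The secondary laboratory endpoint therefore cannot compare symptomless CPK changes between pitavastatin alone and pitavastatin with RO7049389.

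This is a modest gap in a descriptive safety endpoint. It does not affect the primary pharmacokinetic analysis, and symptomatic muscle events remain covered. The conclusion rests on reading the Appendix 4 restriction literally, on the Schedule of Activities not restoring the test, and on CPK being a muscle enzyme. It does not depend on any assumed event rate. It is worth correcting because the blood for a matched comparison is already drawn.

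**What to change.** In Appendix 4, Table 1, delete the screening-only restriction after creatinine phosphokinase (and correct the name to creatine phosphokinase). CPK is then reported from the chemistry samples already scheduled:

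- Day -1 of each period, as that period's baseline;
- Period 1 Day 4 and Period 2 Day 7, as the matched values about 72 hours after pitavastatin;
- follow-up.

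Period 2 Day 4 would come with the same change, but its time relative to dosing should be stated before it is interpreted. Summarise CPK and its change from the period baseline by period, as descriptive statistics only.

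The cost is one more analyte on existing blood, with no new visit or puncture. Some incidental, exercise-related rises will need interpretation; the 72-hour ban on strenuous exercise before laboratory draws (Section 5.3.3) limits these.

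If the sponsor prefers to keep the restriction, the protocol should give the reason and state that the laboratory endpoint does not cover CPK after dosing.

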**Table 1 Protocol-Required Safety Laboratory Assessments (cont.)**

• Hormone	• FSH (females only to confirm post-menopausal status).
• Pregnancy Test	• Serum or plasma beta-human chorionic gonadotropin ( $\beta$ -HCG) at screening, urine on all other occasions (females only). If urine is positive, then need confirmatory serum or plasma test.
• Urinalysis	• Dipstick: pH, glucose, protein, blood, and leucocytes • If there is a clinically significant positive result (confirmed by a positive repeated sample), urine will be sent to the laboratory for microscopy and culture. If there is an explanation for the positive dipstick results (e.g., menses), it should be recorded and there is no need to perform microscopy and culture. • Microscopic examination (sediment, RBCs, WBCs, casts, crystals, epithelial cells, bacteria), if blood or protein is abnormal.
• Urine drug screen	• Cannabinoids, amphetamines, methamphetamines, opiates, methadone, cocaine, benzodiazepines, and barbiturates.
• Cotinine	• Cotinine test as per local practice.
• Alcohol	• Alcohol breath test.

The results of each test must be entered into the CRF.

Investigators must document their review of each laboratory safety report.

### **Additional Statistical Considerations for Clinical Laboratory Data**

- Standard Reference Ranges and Transformation of Data

Roche standard reference ranges, rather than the reference ranges of the Investigator, will be used for all parameters. For most parameters, the measured laboratory test result will be assessed directly using the Roche standard reference range. Certain laboratory parameters will be transformed to Roche's standard reference ranges.

A transformation will be performed on certain laboratory tests that lack sufficiently common procedures and have a wide range of Investigator ranges, e.g., enzyme tests that include AST, ALT, and alkaline phosphatase and total bilirubin. Since the standard reference ranges for these parameters have a lower limit of zero, only the upper limits of the ranges will be used in transforming the data.

- Definition of Laboratory Abnormalities

For all laboratory parameters included, there exists a Roche predefined standard reference range. Laboratory values falling outside this standard reference range will be labeled “H” for high or “L” for low in participant listings of laboratory data.

In addition to the standard reference range, a marked reference range has been predefined by Roche for each laboratory parameter. The marked reference range is broader than the standard reference range. Values falling outside the marked reference range that also represent a defined change from baseline will be considered marked laboratory abnormalities (i.e., potentially clinically relevant). If a baseline value is not available for a participant, the midpoint of the standard reference range will be used as the participant’s baseline value for the purposes of determining marked laboratory abnormalities. Marked laboratory abnormalities will be labeled in the participant listings as “HH” for very high or “LL” for very low.

